8.3.2 Other efficacy biomarkers

Other efficacy assessments will include:

- Apo B, Lp(a), non-HDL-C, total cholesterol, triglycerides, HDL-C, VLDL-C, Apo A1, PCSK9

Samples for these additional efficacy biomarkers will be collected on Days 1, 90 [REDACTED], 150, 330, 360, 510 and 720 ([Table 8-1](#)).

After randomization (Day 1) until the Day 360 visit, the results from the efficacy laboratory assessments must be blinded to participants, investigator staff, persons performing the assessments, and the CTT.

[REDACTED]

[REDACTED]

[REDACTED]

[REDACTED]

[REDACTED]

8.3.5 Appropriateness of efficacy assessments

LDL-C reduction, which is an effect of the mechanism of action of inclisiran, is a well-defined biomarker and standard assessment in clinical trials, and the primary endpoint of the study. LDL-C reduction is an accepted surrogate for CV risk reduction, e.g. for statins and PCSK9-blocking monoclonal antibodies. While multiple factors contribute to the development of ASCVD, strong and consistent evidence from genetics, epidemiology, Mendelian randomization studies, and randomized trials, have established that among these factors, LDL-C is not merely a biomarker of increased risk, but a causal and modifiable factor in ASCVD ([Ference et al 2017](#)).

Laboratory tests and other assessments related to the secondary [REDACTED] are in line with the expected efficacy of inclisiran. [REDACTED]
[REDACTED]

8.4 Safety

Safety assessments are specified below, with the Assessment Schedule ([Table 8-1](#)) detailing when each assessment is to be performed.

For details on AE collection and reporting, refer to the AE section.

A complete physical examination will be performed at the screening visit, the Day 330 visit and at the Study Completion (EOS) visit. An abbreviated physical examination will be performed at other study visits detailed in [Table 8-1](#). Details on what is included in the complete and abbreviated physical exams and the requirements to perform vital signs assessment and height / weight measurements are provided in [Table 8-2](#).

Table 8-2 Assessments & Specifications

Assessment	Specification
Physical examination	
A complete physical examination will include the examination of height, weight, general appearance, skin, neck (including thyroid), eyes, ears, nose, throat, lungs, heart, vital signs, abdomen, back, lymph nodes, extremities, vascular, and neurological. If indicated based on medical history and/or symptoms, rectal, external genitalia, breast, and pelvic exams will be performed.
 
Tanner staging (Section 8.4.4.1) will additionally be performed at selected visits.
 
A short physical examination will include the examination of general appearance and vital signs as well as other examinations based on Investigator discretion. Height and weight will additionally be assessed as per the Schedule of Assessment.
 
Information for all physical examinations must be included in the source documentation at the study site. Clinically relevant findings that are present prior to informed consent signature must be recorded on the appropriate eCRF that captures Medical history. Significant findings made after informed consent signature, which meet the definition of an AE, must be recorded as an AE.

Vital signs	
Vital signs include blood pressure and pulse measurements. After the participant has been sitting for five minutes, with back supported and both feet placed on the floor, systolic blood pressure (SBP) and diastolic blood pressure (DBP) will be measured three times using an automated validated device, e.g. OMRON, with an appropriately sized cuff. The repeat sitting measurements will be made at 1 - 2 minute intervals and the mean of the three measurements will be used. In case the cuff sizes available are not large enough for the participant's arm circumference, a sphygmomanometer with an appropriately sized cuff may be used.
 
Clinically notable vital signs are defined in Section 16.2 (Appendix 2).

Height and weight	Height in centimeters (cm) and body weight (to the nearest 0.1 kilogram (kg) in indoor clothing, but without shoes) will be measured. Height should be taken using a calibrated stadiometer.

8.4.1 Laboratory evaluations

Specimens will be obtained at the time points detailed in the Assessment Schedule ([Table 8-1](#)). Details on what is included in hematology, chemistry, sexual hormones, and urinalysis

laboratory evaluations are provided in [Table 8-3](#). Efficacy laboratory assessments (e.g. LDL-C) are described in [Section 8.3](#).

Central laboratory(ies) will be used for analysis of all specimens collected, with the exception of urine pregnancy tests, which will be done locally (using testing materials supplied by the central laboratory). Serum pregnancy tests at screening will be done by the central laboratory. Details on the collections, shipment of samples and reporting of results by the central laboratory are provided to investigators in a Laboratory Manual.

Clinically notable laboratory findings are defined in [Section 16.2](#) (Appendix 2).

A table, which provides the maximum, allowable blood-draw volumes by weight, can be found in [Section 16.7](#) (Appendix 7). The Laboratory Manual will also provide details about prioritization when blood volume is restrictive.

Table 8-3 Laboratory Assessments

Test Category	Test Name
Hematology	Hemoglobin, hematocrit, red blood cell (RBC) count, mean cell hemoglobin (MCH), mean corpuscular volume (MCV), mean corpuscular hemoglobin concentration (MCHC), white blood cell (WBC) count with differential (neutrophils, basophils, eosinophils, monocytes, lymphocytes), platelet count
Chemistry	Full chemistry: AST, ALT, ALP, GGT, total bilirubin, direct and indirect bilirubin (if total bilirubin >2xULN), C(P)K, bicarbonate, uric acid, creatinine, blood urea nitrogen (BUN), eGFR*, sodium, potassium, calcium, phosphate, chloride, albumin, total protein, glucose (fasting)**, HbA _{1C} Limited chemistry: ONLY: AST, ALT, ALP, GGT, total bilirubin [fractionated bilirubin (if total bilirubin >2x ULN)], C(P)K, creatinine, eGFR*, glucose (fasting)**, HbA _{1C}
Anti-drug antibodies	see Section 8.4.1.1
Sexual hormones	Gonadal hormones (estradiol for females and testosterone for males), luteinizing hormone (LH), follicle-stimulating hormone (FSH), cortisol and dehydroepiandrosterone (DHEA)
Urinalysis	Dipstick measurements for: specific gravity, pH, glucose, protein (total), ketones, bilirubin, urobilinogen, nitrite, hemoglobin (blood), leukocytes esterase If dipstick measurement results are positive (abnormal), microscopic examination will be performed
Pregnancy test	Serum / Urine pregnancy test (see Section 8.4.3)
Other	Tryptase (only as required***)

* eGFR will be calculated using the Schwartz age-specific eGFR formula as follows:

- For height in cm and serum creatinine (sCr) in mg/dL: eGFR (mL/min/1.73 m²) = 0.413 x (height/sCr)
- For height in cm and sCr in µmol/L: eGFR (mL/min/1.73²) = 36.5 x (height/sCr)

** Diagnosis of diabetes based on FPG should be verified by a repeat FPG within 6 weeks of the initial observation

*** Should a participant develop anaphylaxis on days when inclisiran is injected, the investigator will need to collect a blood sample for tryptase within 30 minutes of the onset of anaphylaxis (or as soon as possible)

8.4.1.1 Anti-drug antibodies

Serum samples for the analysis of formation of ADA will be collected at the time points detailed in the Assessment Schedule ([Table 8-1](#)).

On Day 1, ADA serum samples will be collected prior to injection and 4 hours after injection. At all other visits, one sample only will be collected.

The results from ADA after the first administration of study drug until the Day 360 visit must be blinded to participants, investigator staff, persons performing the assessments, and the CTT.

Instructions to be followed regarding sample collection, numbering, processing and shipment are outlined in a Laboratory Manual.

8.4.2 ECG

ECGs will be done with local ECG machines. ECGs must be recorded (after 10 minutes rest in the supine position to ensure a stable baseline). The preferred sequence of CV data collection during study visits is ECG collection first, followed by vital signs, and blood sampling. The Fridericia QT correction formula (QTcF) should be used for clinical decisions.

Single 12 lead ECGs are collected. The original ECGs on non-heat-sensitive paper and a copy (if original ECG done on heat sensitive paper), appropriately signed, must be collected and archived at the study site.

For any ECGs with participant safety concerns, two additional ECGs must be performed to confirm the safety finding. A monitoring or review process should be in place for clinically significant ECG findings throughout the study and especially before administration of study treatment.

Any identifier details must be redacted e.g. participant initials, date of birth.

Clinically significant abnormalities must be recorded on the eCRF as either Medical history/Current medical condition or AEs as appropriate.

8.4.3 Pregnancy

Females of child-bearing potential are defined as all females physiologically capable of becoming pregnant. This includes female adolescent participants who are menarchal or who become menarchal during the study.

Serum/urine pregnancy tests will be performed for all female adolescents of child-bearing potential according to the Assessment Schedule ([Table 8-1](#)). A positive urine pregnancy test should be confirmed with a serum pregnancy test. Additional pregnancy tests may be performed at the investigator's discretion during the study and/or if requested by local requirements.

Participants becoming pregnant must be discontinued from study drug. However, a participant may choose to remain in the study should she become pregnant, and be followed according to the protocol-defined study visits.

All menarchal adolescents and their parent(s)/legal representative(s) should be informed about the potential risks of pregnancy and the need to prevent pregnancy during the study.

It is important to be sensitive in introducing this issue, as understanding and comprehension of puberty, sexual activity, pregnancy and contraception is influenced by age as well as, factors such as precocity, socio(educational) economic and familial background. These discussions with the participant and her parent(s)/legal representative(s) are therefore best performed by investigators familiar with the adolescent participant and her family and should be guided by

requirements of the local regulatory authorities. These discussions should take into account the socio-economic, cultural factors and religious beliefs of the adolescent participant and her family. The investigator should also discuss the management of the pregnancy test results with the participant and her parent(s)/legal representative(s). The privacy of the participant should be considered in accordance with the local law and ethics.

8.4.4 Other safety evaluations

8.4.4.1 Pubertal development

In addition to the assessment of height, weight and sexual hormones (see [Section 8.4.1](#)), the following parameters will be monitored to evaluate pubertal development, at the time points detailed in the Schedule of Assessment ([Table 8-1](#)):

- Menarche (in females)
- Tanner staging of sexual development (in males and females)

Tanner staging will be performed by a physician who (re-)familiarized him/herself with the Tanner stage assessment (in case needed). The results (stages 1-5 for the respective characteristics) will be recorded on an appropriate eCRF. Once a participant reaches Tanner stage 5, evaluations can be discontinued. For females, the date of menarche will also be recorded on an appropriate eCRF.

8.4.4.2 Neurological evaluation

A full neurological evaluation will be performed as per the Schedule of Assessment ([Table 8-1](#)). This should include assessment of motor function, sensory function, tone and reflexes and cerebellar function as detailed in [Section 16.5](#) (Appendix 5).

Clinically significant abnormalities must be recorded on the eCRF as either Medical history/Current medical condition or AEs as appropriate.

8.4.4.3 Injection site reactions

Injection site reactions (ISRs) should be monitored at each visit from the randomization (Day 1) visit onwards ([Table 8-1](#)) and through additional contacts with the participant between visits as needed. ISRs including individual signs or symptoms at the injection site following study treatment administration should be recorded on an appropriate eCRF page. Every effort should be made to follow up with the participant until resolution of the ISR.

8.4.4.4 Anaphylactic reactions

Potential anaphylactic reactions should be assessed by Sampson criteria (see [Section 16.6](#) (Appendix 6)). If Sampson criteria are positive, confirmation by elevation of tryptase in blood plasma should be obtained within 30 minutes of the onset of anaphylaxis (or as soon as possible).

8.4.4.5 Hyperglycemia-related events

Laboratory results and newly added concomitant medications should be checked for potential hyperglycemia-related AEs.

'New onset of diabetes' should be reported as AE on the eCRF in participants with no medical history of diabetes when:

- HbA_{1c} becomes $\geq 6.5\%$ and/or
- Two consecutive values of FPG are ≥ 126 mg/dL (7.0 mmol/L)
- If a new concomitant medication for control of plasma glucose is added, further information to assess for a diagnosis of new onset diabetes will need to be collected

'Worsening of glycemic control' should be reported as AE on the eCRF in participants with a medical history of disease (HbA_{1c} $\geq 6.5\%$ at baseline) when:

- HbA_{1c} increases from baseline $>0.5\%$
- New concomitant medication or increase in dose of current antidiabetic therapy is initiated to improve the control of plasma glucose level

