7. Any uncontrolled or serious disease, or any medical or surgical condition, that may either interfere with participation in the clinical study, and/or put the participant at significant risk (according to investigator's [or delegate's] judgment) if he/she participates in the clinical study
8. An underlying known disease, or surgical, physical, or medical condition that, in the opinion of the investigator (or delegate) might interfere with interpretation of the clinical study results
9. Heterozygous FH
10. Any condition that according to the investigator could interfere with the conduct of the study, such as but not limited to:
 - Participants who are unable to communicate or to cooperate with the investigator
 - Unlikely to comply with the protocol requirements, instructions, and study-related restrictions (eg, uncooperative attitude, inability to return for follow-up visits, and improbability of completing the study)
 - Have any medical or surgical condition, which in the opinion of the investigator would put the participant at increased risk from participating in the study

- Persons directly involved in the conduct of the study

11. Treatment with other investigational medicinal products or devices within 30 days or five half-lives, whichever is longer

12. Planned use of other investigational products or devices during the course of the study

13. Hypersensitivity to any of the ingredients of inclisiran

14. Known history of alcohol and/or drug abuse

15. Secondary hypercholesterolemia, e.g. hypothyroidism or nephrotic syndrome

16. Major adverse cardiovascular events within 1 month prior to randomization

17. Severe concomitant non-cardiovascular disease that carries the risk of reducing life expectancy to less than 2 years

18. History of malignancy that required surgery (excluding local and wide-local excision), radiation therapy and/or systemic therapy during the 3 years prior to randomization

19. Poorly controlled diabetes mellitus (i.e. hemoglobin A1c (HbA_{1c}) >10.0 %)

20. Previous participation in this study

6 Treatment

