12.8 Sample size calculation

12.8.1 Primary endpoint(s)

The sample size for this study was selected based on feasibility.

13 Ethical considerations and administrative procedures

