2.7.4 Diabetes assessment

Diabetes will be assessed by the analysis of:

- TEAEs
- Change in glucose-related laboratory values over time
- Shifts from baseline in glucose control category and
- Incidence of post-baseline new onset of diabetes

Note that diabetes related tables dealing with the fasting plasma glucose parameter will require the lab sample to be taken fasting. Samples taken while the subject was not fasted will not be analyzed.

Unless otherwise specified, baseline of fasting plasma glucose will be defined as the average of Screening and Day 1 assessments. If one fasting plasma glucose value is missing (Screening or Day 1), the baseline will be based on the available data. For HbA1c, the Day 1 assessment will be considered as baseline. If missing, then the baseline will be based on the assessment at screening.

Diabetes TEAE

New onset/worsening of diabetes will be identified by the search criteria specified in [Appendix 5.4](#). The analysis will be performed for all subjects and then by baseline diabetes status. A participant will be identified as being diabetic at baseline if the medical history notes that the subject is diabetic or the baseline HbA1c value is $\geq 6.5\%$ or the baseline fasting plasma glucose is ≥ 126 mg/dL. This summary will be provided by treatment and Part.

Change in Glucose-related Laboratory Values over Time

This analysis only utilizes laboratory data (fasting plasma glucose and HbA1c). The change from baseline to the last on-treatment observation and the worst on-treatment observation will be summarized by treatment and Part, separately for fasting plasma glucose and HbA1c for all participants and then by baseline glucose control status. Baseline glucose control status will be identified separately for fasting plasma glucose and HbA1c using the values provided in the table below (note that medical history will not be considered for this analysis). Figures will also be created showing change in mean fasting plasma glucose and HbA1c values over time by baseline glucose control status.

Parameter	Baseline Glucose Control Status (Laboratory Values)
Fasting Plasma Glucose	<100 mg/dL
	≥ 100 to < 126 mg/dL
	≥ 126 mg/dL
HbA1c	<5.7%
	≥ 5.7 to $< 6.5\%$
	$\geq 6.5\%$

Shifts from Baseline in Glucose Control Category

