***For post-baseline categories, if the post-baseline two consecutive fasting plasma glucose measurements fall in separate categories, or if only one post-baseline fasting plasma glucose measurement is available, then the post-baseline glucose control category will be defined based on the HbA1c measurement only. If HbA1c value is missing and two consecutive fasting plasma glucose measurements fall in separate categories, the lower category will be used to determine the post-baseline category.

Incidence of Post-baseline New-Onset of Diabetes

The number of participants who shift from no diabetes at baseline to post-baseline new onset of diabetes will be summarized.

The participants with no diabetes at baseline are those who had no medical history of diabetes in the medical history CRFs, had baseline HbA1c $< 6.5\%$, and had baseline fasting plasma glucose < 126 mg/dL prior to the start of study treatment.

A 4-component analysis will be utilized to detect post-baseline new onset of diabetes. The 4 components are provided below:

- Diabetic TEAEs identified by the SMQ search (see [Section 5.4](#)), or
- Post-baseline fasting plasma glucose ≥ 126 mg/dL on two consecutive occasions, or
- Initiation of anti-diabetic medication at any time post-baseline, or
- At least one post-baseline HbA1c $\geq 6.5\%$.

The number of participants who have any of the 4 components will be summarized (post-baseline new onset of diabetes) by treatment and Part.

This analysis will be performed separately for participants who had normal and impaired glucose control categories at baseline.

- Subjects with normal glucose control status at baseline are those with all the following:
 - No medical history of diabetes.
 - HbA1c $< 5.7\%$ AND fasting plasma glucose < 100 mg/dL at baseline.

Novartis SAP amendment 4	For business use only	Page 29 CKJX839C12302
-----------------------------	-----------------------	--------------------------

- Subjects with impaired glucose control status at baseline are those with all the following:
 - No medical history of diabetes.
 - HbA1c $\geq 5.7\%$ and $< 6.5\%$ (and fasting plasma glucose $< 126 \text{ mg/dL}$) OR fasting plasma glucose $\geq 100 \text{ mg/dL}$ and $< 126 \text{ mg/dL}$ (and HbA1c $< 6.5\%$) at baseline.

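### A participant with known diabetes and baseline HbA1c below 6.5% falls outside both hyperglycemia AE-reporting rules in Protocol 8.4.4.5, so a worsening may be missing from the TEAE-based diabetes summary

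*Protocol*

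**What the plan says.** Protocol 8.4.4.5 tells sites to check laboratory results and newly added medications for hyperglycemia-related AEs, then sets two named rules.

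- *New onset of diabetes* is to be reported "in participants with no medical history of diabetes when" HbA1c reaches 6.5% or two consecutive fasting plasma glucose (FPG) values reach 126 mg/dL. A new glucose-lowering medication prompts collection of further information.
- *Worsening of glycemic control* "should be reported as AE on the eCRF in participants with a medical history of disease", specified in brackets as HbA1c of 6.5% or more at baseline, when HbA1c rises by more than 0.5% from baseline, or antidiabetic therapy is started or increased.

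On entry, exclusion 19 in Protocol 5.2 bars "Poorly controlled diabetes mellitus (i.e. hemoglobin A1c" above 10.0%. Diabetes as such is not excluded.

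Protocol 10.2.3 lists new onset of diabetes, and worsening of glycemic control in diabetics, among the AEs the DMC reviews. It sets no HbA1c floor of its own but refers back to 8.4.4.5.

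SAP 2.7.4 divides participants differently. "A participant will be identified as being diabetic at baseline if the medical history notes that the subject is diabetic", or if baseline HbA1c is at least 6.5%, or if baseline FPG is at least 126 mg/dL. For the new-onset analysis, "The participants with no diabetes at baseline are those who had no medical history of diabetes in the medical history CRFs" and who were below both laboratory limits at baseline.

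**The concern.** The two rules look as if they divide all participants into those without and those with diabetes. They do not, because one is keyed to history alone and the other to history plus a laboratory value. Someone with diagnosed diabetes controlled to below 6.5% has a history, so is not eligible for new onset, and lacks the baseline HbA1c named for worsening.

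At stake is the completeness of one safety topic. SAP 2.7.4 identifies new or worsening diabetes among TEAEs by searching reported events. If no rule asks the site to report a deterioration, that table can be empty for a participant whom the SAP itself labels diabetic, and the DMC topic in Protocol 10.2.3 draws on the same reports.

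**Working it through.** No sample size, power or error rate is involved; Protocol 12.8.1 states that "The sample size for this study was selected based on feasibility". The check is one of coverage.

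**Step 1. Cross the two entry conditions of Protocol 8.4.4.5.**

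| Diabetes history | Baseline HbA1c | New-onset rule | Worsening rule |
|---|---|---|---|
| No | < 6.5% | applies | does not apply |
| No | ≥ 6.5% | applies, but HbA1c is already at the trigger level; the FPG trigger and medication follow-up remain | does not apply |
| Yes | ≥ 6.5% | does not apply | applies |
| Yes | < 6.5% | does not apply | does not apply |

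The last row is uncovered. Exclusion 19 removes only HbA1c above 10.0%, so the row can be reached.

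**Step 2. Follow two illustrative records.** The values are assumed. Both have a diabetes history, and FPG is assumed not to change the category.

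*Record A: HbA1c 6.2% at baseline, 7.4% later.* The rise is 7.4 − 6.2 = 1.2 points, above 0.5, and the later value is above 6.5%. New onset fails on history; worsening fails because 6.2% is below 6.5%. In the SAP:
- The participant is diabetic at baseline and outside the new-onset analysis (2.7.4).
- The TEAE summary includes the event only if the site reported it.
- The glucose-control shift analysis (2.7.4), which ignores history, shows Impaired to Diabetes, and this is tallied as worsened.
- The HbA1c shift table (2.7.3) moves from the middle to the top category.
- The notable-value count for HbA1c ≥ 6.5% (2.7.3 with Table 5-1) includes it, since the baseline did not meet that criterion.
- The HbA1c change summaries include the 1.2 points.

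*Record B: HbA1c 5.8% at baseline, 6.4% later.* The rise is 6.4 − 5.8 = 0.6 points, again above 0.5. Neither protocol rule applies. Both values lie between 5.7% and 6.5%, so the glucose-control shift is Impaired to Impaired, tabulated as no change. The HbA1c shift table also stays in one category. The notable-value count does not include the record, because the baseline already met that band. Only the HbA1c change summaries and the listings carry it.

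**Step 3. Weight of one case.** A 2:1 split of about 12 gives about 8 and 4. One participant is 1/8 = 12.5% of the inclisiran group or 1/4 = 25% of the placebo group. This is the weight of a single case if there is one. It does not estimate an under-count.

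**Step 4. Does the SAP definition close the gap?** The SAP's diabetic group is history OR HbA1c ≥ 6.5% OR FPG ≥ 126 mg/dL. Its no-diabetes group is no history AND HbA1c < 6.5% AND FPG < 126 mg/dL. Each is the exact complement of the other, so used together they cover everyone once. Widening the worsening rule alone would not do this: a participant with no history and a baseline HbA1c of 6.8% would fall under both rules, against SAP 2.7.4.

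**The case against.** The strongest reply is that little is lost. Protocol 8.4.4.5 opens with a check of laboratory results and new medications that is not limited by history. Protocol 10.1.1 requires review of significant changes from baseline and makes an abnormal value an AE if it causes signs or symptoms, is clinically significant or requires therapy. A deterioration that leads to new or increased antidiabetic treatment would meet the last of these. The SAP also tabulates the laboratory data whatever the site reports.

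Most of this stands. A reader might infer that the deterioration goes unreported altogether, or that the SAP counts worsening only through TEAEs. The documents support neither: 10.1.1 is a partial backstop, and the history-blind shift analysis has its own worsened category, which captures record A. What remains is an untreated rise without symptoms that the site judges not clinically significant. It has no objective reporting trigger, and if it stays within one HbA1c category, as in record B, the shift tables do not show it either.

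It can also be said that the bracket in the worsening rule is only illustrative. That reading would close the gap, but the text does not state it, and sites could apply the rule differently.

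**Conclusion.** The point holds as a gap in the AE-reporting rules. A participant with a diabetes history and baseline HbA1c below 6.5% meets neither named rule, while Protocol 10.2.3 and SAP 2.7.4 speak of or treat that participant as diabetic. The consequence is limited to possible absence from the TEAE-based diabetes summary; the laboratory data remain in the SAP's summaries, with the within-category limitation shown by record B.

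The practical size is probably small. About 12 participants are planned, and the documents do not say whether any has diabetes, so it cannot be shown that any event is missed. The conclusion assumes that the bracketed HbA1c value is read as a condition. This is a minor point, worth correcting because the rule misses part of its own target group and the remedy is already in the SAP.

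**What to change.** Reconcile Protocol 8.4.4.5, Protocol 10.2.3 and SAP 2.7.4 on one definition of diabetes at baseline. Use the existing SAP definition (history, or HbA1c ≥ 6.5%, or FPG ≥ 126 mg/dL) for the worsening rule, and the SAP's no-diabetes group for the new-onset rule. Change both together so that the groups are exhaustive and do not overlap. Leave the existing triggers as they are. Tell sites which baseline values apply: SAP 2.7.4 averages screening and Day 1 for FPG and takes Day 1 for HbA1c.

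The cost is one phrase in each rule, with no new threshold and no new data. SAP 2.5.6 already refers to the small placebo group, so enrolment appears complete and an amendment may not be practical. A SAP edit cannot create site-reported AEs. In that case, add a SAP listing, by treatment and Part, of participants diabetic at baseline by the SAP definition who meet the existing worsening triggers, derived from the laboratory and medication data already collected. The downside is possibly one or two more AEs or listing entries.
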